3.5.6 Multiplicity

A Hochberg procedure will be applied to final analysis of RR and DCR for internal decision purposes based on the ipilimumab-naïve patients treated at 10 mg/kg in Part B enrolled through Amendment 4. The overall type I error rate is set at 5% (one-sided),

i.e., the trial is considered to have reached the efficacy objective if the two corresponding p-values for testing the null hypothesis (RR=10% and DCR=30%) are less than 5% OR either one is less than 2.5%. There are two planned interim analyses for administrative purposes. There is no intention to terminate the study early for efficacy, and no multiplicity adjustment is applied to the interim analyses.

The predictive biomarker hypothesis on concordance between tumor volume change and PD-L1 will be formally tested at a type I error rate of 2.5% (one-sided) separately for each part of the study, irrespective of the outcome from efficacy analyses. Once the null hypothesis is rejected, a step-down procedure may be applied to the testing of other biomarker hypotheses prospectively specified before the end of the study. While additional exploratory analyses will be conducted to evaluate alternative predictive biomarkers, there is no multiplicity control of such analyses and no formal conclusion can be made.

The efficacy hypothesis on anti-tumor activity of pembrolizumab (MK-3475) is tested at 5% (one-sided) for Part B ipilimumab-treated (non-randomized), at 10% (one-sided) for Part C, and at 2.5% (one-sided) for all other populations. Between-dose comparisons are all conducted at 20% (two-sided), or equivalent 10% (one-sided) for sample size and power calculation purpose below, except for Part B (10 mg/kg Q3W vs 10 mg/kg Q2W) which is conducted at 5% (two-sided).

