3.5.7 Sample Size and Power Calculations

Part B ipilimumab-naïve enrolled through Amendment 4 (non-randomized)

With 61 ipilimumab-naïve patients treated at the 10 mg/kg in both Q2W and Q3W, the study has approximately 97% power to detect an effect size of RR=25% or DCR=50% under the null hypothesis of RR=10% and DCR=30%, or >99% power to detect an effect size of RR=30% or DCR=55%, at a type I error rate of 5% (one-sided) based on the Hochberg procedure. For the subgroup of patients on a dose /schedule, the corresponding powers to the two effect sizes are respectively 87% and 97% when the sample size is 40, 76% and 91% when the sample size is 30, and 44% and 62% when the sample size is 15.

Part B ipilimumab-treated enrolled through Amendment 4 (non-randomized)

With 40 patients treated at 10 mg/kg, the study has approximately 92%/98% power to rule out a $\leq 5\%$ spontaneous RR (null hypothesis) when the true RR is 20%/25% at the 5% type I error rate (one-sided). With true RR assumed to be 20%/25%, the corresponding power is 75%/90% when sample size is 30 and 59%/78% when sample size is 20 at Q3W or Q2W.

Part B ipilimumab-refractory enrolled after Amendment 04 (randomized: 10 mg/kg Q3W vs 2 mg/kg Q3W)

With 80 ipilimumab-refractory patients at each dose level, the study has ~85% (or 96%) power to detect a 15% (or 20%) difference in RR between the two doses at the 10%

type I error rate (one-sided) when the RR in the inferior arm is 10%. A p-value of 10% approximately corresponds to a 7% empirical difference in RR.

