3.5.9 Interim Analyses

Part B Ipilimumab-Naïve Patients (non-randomized)

The study will have two planned interim analyses for internal decision purpose in ipilimumab-naïve patients treated at 10 mg/kg in Part B enrolled through Amendment 4 (non-randomized). The endpoints in these interim analyses are RR and DCR at week 12. There is no intention to stop the trial for efficacy at the first or second interim analysis. The accrual for Part B is expected to be fast. Should it be slower than expected, one additional interim analysis may be added. The decision rules at the interim analyses serve as guidance and are non-binding. In absence of a control arm, outcomes in this single arm study have to be interpreted with caution, both at interim and final analyses.

The first planned interim analysis will occur when the first 11 patients are evaluable for response assessment at 12 weeks (i.e., have either completed the first tumor re-assessment at week 12 or discontinued the study before week 12). To prevent undue over-enrollment in case the futility bar will be crossed and the study may get terminated early, enrollment of the first 13 MEL patients in Part B will be restricted to ipilimumab-naïve patients.

The futility bar has been set at zero objective response in 11 evaluable patients AND disease control in <5 patients at week 12. This decision criterion has 51% power to rule out the null hypothesis, 89% power to rule out the intermediate effect size and 95% power to rule out the high effect size.

Enrollment will not be stopped for purpose of the first interim futility analysis. Accordingly, approximately 30-38 patients may have been enrolled when the data from that analysis will become available, based on current accrual rate projections. This will include patients without and with prior treatment with ipilimumab.

If the futility bar will be crossed at the first futility analysis (i.e., in case of $\geq 1/11$ responses OR $\geq 5/11$ patients with disease control), enrollment will continue to the

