planned sample size for response assessment. If the futility bar will not be crossed at 11 patients, enrollment will be temporarily stopped until all patients who have been already enrolled at the time will have completed their week 12 disease assessment. The number of objective responses or disease control required in this second interim analysis to continue enrollment to the full planned sample size will depend on the number of available patients. In addition, preliminary biomarker data may be taken into account in the decision to continue or stop enrollment.

The second planned interim analysis will be performed when all patients have completed tumor assessment at Week 12 only if the primary objective of the analysis is not met earlier. The primary purpose of this analysis is to provide an early assessment of overall anti-tumor activity, for administrative purpose (e.g., planning of a subsequent study in MEL). A Hochberg procedure with type I error rate of 5% (one-sided) will be applied to assist with the decision. Table 3-6 shows outcomes of interest that are on the borderline of the rejection zone of the null hypothesis, based on various hypothetical sample sizes of evaluable ipilimumab-naïve patients.

Table 3-6

Efficacy Outcome of Interest in Ipilimumab-Naïve Population
at the Second Planned Interim Analysis

Sample size	RR at week 12 (null=5%)		DCR at week 12 (null=30%)	
	Patients with response (%)	Nominal p-Value	Patients with disease control (%)	Nominal p-Value
25	4 (16%)	3.4%	12 (48%)	4.4%
30	5 (17%)	1.6%	14 (47%)	4.0%
35	5 (14%)	2.8%	16 (46%)	3.6%
40	6 (15%)	3.8%	18 (45%)	3.2%

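### Part B ipilimumab-naïve: the Table 3-6 p-value for 6/40 and the subgroup powers at n=30 and n=40 do not follow from the plan's own Hochberg rule

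*Combined protocol and SAP*

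**What the plan says.** Section 3.5.6: "The overall type I error rate is set at 5% (one-sided") for RR and DCR together in the ipilimumab-naïve patients treated at 10 mg/kg and enrolled through Amendment 4. The objective is reached if "the two corresponding p-values for testing the null hypothesis (RR=10% and DCR=30%) are less than 5% OR either one is less than 2.5"%. Section 3.5.5.1 bases the one-sided p-values on the binomial distribution and extends the same analysis to week 12.

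Section 3.5.7 gives power "at a type I error rate of 5% (one-sided) based on the Hochberg procedure" for two effect sizes, RR 25%/DCR 50% and RR 30%/DCR 55%:

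- 61 patients: about 97% and above 99%
- Subgroups: "87% and 97% when the sample size is 40, 76% and 91% when the sample size is 30"
- 15 patients: 44% and 62%

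For the second interim analysis, section 3.5.9 says "A Hochberg procedure with type I error rate of 5% (one-sided) will be applied to assist with the decision". It introduces Table 3-6 as showing "outcomes of interest that are on the borderline of the rejection zone of the null hypothesis". The week-12 nulls there are RR 5% and DCR 30%. The row for 40 patients lists 6 responses (15%) with p = 3.8%, and 18 patients with disease control (45%) with p = 3.2%.

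**The concern.** Table 3-6 looks wrong before any calculation. It gives 15% of 40 patients a larger p-value than 14% of 35 (2.8%), although a higher rate in a larger sample must be stronger evidence against the same null. The printed 3.8% lies above the 2.5% single-endpoint threshold, so a reader would conclude that 6/40 also needs the DCR bar of 18/40.

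The subgroup powers raise a separate question: whether they were calculated under the rule that section 3.5.7 names. If they were not, the plan overstates what a single dose/schedule group can show. Section 3.5 states that no separate SAP will be issued, so these are the figures of record.

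**Working it through.** **Table 3-6, RR column.** Inputs: week-12 null 5% and the counts in the table. Formula: p = P(X ≥ k), X ~ Bin(n, 0.05).

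| n | printed count | printed p | exact p | exact p, one response fewer |
|---|---|---|---|---|
| 25 | 4 | 3.4% | 3.41% | 12.71% |
| 30 | 5 | 1.6% | 1.56% | 6.08% |
| 35 | 5 | 2.8% | 2.90% | 9.58% |
| 40 | 6 | 3.8% | **1.39%** | 4.80% |

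The first three rows reproduce, apart from a last-digit slip at 5/35, so the table uses the exact binomial test. The DCR column reproduces as well: 4.42%, 4.01%, 3.59%, 3.20%. In the first three RR rows the listed count is the smallest with p below 5%; at n=40 that count is 5, not 6. Six responses give 1.39% and five give 4.80%, so no count at n=40 gives 3.8%.

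The outcomes read differently because of this cell are exactly 6 responses with fewer than 18 patients in disease control. With 40 evaluable patients, and responders counted within disease control, their probability is 0.9% at RR 5%/DCR 30%, 7.6% at 15%/45% and 4.2% at 20%/50%.

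**Dependence between RR and DCR.** Power under the rule depends on how the two endpoints move together, which the plan does not state. Disease control includes responders, so the natural joint model is

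P(D = d, R = r) = Bin(d; n, p_D) × Bin(r; d, p_R/p_D).

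Two sets of the plan's own figures test this.

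- First interim (11 patients; futility is no response and fewer than 5 with disease control). Section 3.5.9 says "This decision criterion has 51% power to rule out the null hypothesis, 89% power to rule out the intermediate effect size", and 95% for the high effect size. The chance of continuing is 50.9%, 88.9% and 94.8% with nested endpoints, against 55.1%, 93.4% and 97.6% with independent endpoints.
- n=15. The smallest counts below 5% are RR 5/15 (1.27%) and DCR 9/15 (1.52%); 4/15 gives 5.56% and 8/15 gives 5.001%. No attainable p-value lies between 2.5% and 5%, so only the dependence matters here. Nested gives 43.9%/61.6% (stated 44%/62%); independent gives 52.2%/71.8%.

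Nesting is what the plan used in both places.

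**Subgroup power.** Nulls RR 10% and DCR 30%; success if both p < 5% or either p < 2.5%. Smallest counts meeting each threshold:

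| n | RR, p<5% | RR, p<2.5% | DCR, p<5% | DCR, p<2.5% |
|---|---|---|---|---|
| 30 | 7 (2.58%) | 8 (0.78%) | 14 (4.01%) | 15 (1.69%) |
| 40 | 8 (4.19%) | 9 (1.55%) | 18 (3.20%) | 19 (1.48%) |
| 61 | 11 (3.81%) | 12 (1.65%) | 25 (4.43%) | 26 (2.46%) |

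Summing the joint probabilities over the success region:

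| n | stated | exact, nested | stated minus exact (points) | exact, independent |
|---|---|---|---|---|
| 15 | 44% / 62% | 43.9% / 61.6% | 0.1 / 0.4 | 52.2% / 71.8% |
| 30 | 76% / 91% | 71.0% / 88.1% | **5.0 / 2.9** | 80.3% / 94.7% |
| 40 | 87% / 97% | 84.1% / 95.8% | **2.9** / 1.2 | 91.7% / 98.8% |
| 61 | 97% / >99% | 96.0% / 99.6% | 1.0 / – | 98.9% / >99.9% |

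A simulation of 1,000,000 trials per setting gives 70.9%/88.1% at n=30 and 84.1%/95.8% at n=40.

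**Search for a rule that fits.** With the Hochberg rule, neither mid-p values nor normal approximations (with or without continuity correction) give all the printed figures. A looser rule, either exact p below about 3.3%, gives 86.6%/96.5%, 76.1%/90.9% and 43.9%/61.6% at n=40, 30 and 15, which matches all six subgroup figures after rounding. It counts 7/30 responses (p = 2.6%) and 18/40 with disease control (p = 3.2%) as successes on their own, which section 3.5.6 does not allow. Whether that rule was actually used cannot be established from the documents.

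**The case against.** The arithmetic is not in dispute; the case against concerns weight and certainty.

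- **Use of the table.** Table 3-6 illustrates hypothetical sample sizes, and the p-value at the interim would be calculated from the data. As printed, the n=40 row is positive (3.8% and 3.2%, both below 5%), and it stays positive at 1.4%. A misreading needs 40 evaluable patients, exactly 6 responses, fewer than 18 with disease control, and reliance on the printed value. The analysis is administrative, and "The decision rules at the interim analyses serve as guidance and are non-binding". All of this stands and limits the consequence, but the cell is still wrong.
- **Size of the groups.** Table 2-1 lists 41 ipilimumab-naïve patients at 10 mg/kg Q2W and 17 at Q3W, so the largest gap, at n=30, matches neither group. Enrollment is complete, and restated power changes no sample size. This also stands.
- **Unstated dependence.** The first stated powers at n=30 and n=40 lie between the nested and independent results (76% between 71.0% and 80.3%; 87% between 84.1% and 91.7%), so an intermediate dependence might seem to explain them. It does not. Nesting follows from the definition of disease control and reproduces the n=15 and futility figures. Varying the share of responders counted as disease control from 50% to 100% brings no value within 2 points of all six subgroup powers; the best, 90%, still misses by 3.1 points.
- **A different cut-off.** The 3.3% rule fits, so asking which rule was used is reasonable. It is not the rule that section 3.5.7 names, so the inconsistency remains.

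**Conclusion.** The point holds and is minor. The Table 3-6 p-value for 6/40 is 1.4%, not 3.8%; this needs no assumption beyond the exact binomial test that the plan specifies. The error puts the outcome on the wrong side of the 2.5% threshold. Three subgroup powers (76% and 91% at n=30, 87% at n=40) are 5.0, 2.9 and 2.9 points above what the stated rule delivers. This part assumes that responders are nested in disease control, which the plan's own figures support; independent endpoints do not recover the printed values either. The cause of the differences is not known. The overall power at n=61 holds within about 1 point, and no RECIST 1.1 central-review analysis is affected.

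**What to change.** 1. In Table 3-6, n=40, replace the RR entry by 5 (12.5%) with p = 4.8%, which follows the smallest-count pattern of the other rows, or keep 6 (15%) and print 1.4%. Correct 5/35 to 2.9% at the same time.
2. In section 3.5.7, restate the subgroup powers as 71%/88% at n=30 and 84%/96% at n=40.
3. Add one sentence naming the decision rule, the exact binomial test and the nesting of responders within disease control. If a different per-endpoint cut-off was used for the printed powers, say so and reconcile it with section 3.5.6.

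The cost is two table entries, four power figures and one sentence. No sample size, decision rule or primary analysis changes.

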In addition to detecting dose response, we are also interested in testing whether pembrolizumab (MK-3475) is superior to putative chemotherapies in this population. While the spontaneous RR is likely less than 5%, there is no historical data on response rate of chemotherapies in the ipilimumab-refractory population. However, it ranged from 5% to 10% for chemotherapies in three recently completed phase 3 studies (ipilimumab in 1st line melanoma patient, and trametinib and vemurafenib in patients with BRAF V600E mutation). Therefore, it is reasonable to use 10% as the null hypothesis for testing the anti-tumor activity of pembrolizumab (MK-3475) against putative chemotherapies in this population. With 80 patients treated at a dose level, the study has 93% power to reject the null hypothesis at a type I error rate of 2.5% (one-sided) when the true response rate of pembrolizumab (MK-3475) is 25%. A p-value of 2.5% approximately corresponds to a 19% empirical response rate when sample size is 80. With the prevalence of high PD-L1 projected to be from 40% to 60%, the number of high PD-L1 patients treated at a dose level ranges from 32 to 48 and the half-width of the 95% confidence intervals for RR at a dose level approximately ranges from 14% to 17% when the empirical RR in the high PD-L1 group is 50% and from 13% to 16% when the empirical RR in the high PD-L1 group is 70% or is 30%. With 32 to 48 patients in the PD-L1 high group, the study has 79% to 94% power to reject the null hypothesis of 10% RR at type I error rate of 2.5% (one-sided) when the true RR is 30%.

Part C NSCLC (single arm)

With 35 NSCLC patients treated at RP2D, the study has approximately 80% power to rule out a $\leq 9\%$ RR (null hypothesis) when the true RR is 22% at the 10% type I error rate (one-sided).

Part D ipilimumab-naïve enrolled after Amendment 04 (randomized)

With 44 patients treated at 2 mg/kg and 44 treated at 10 mg/kg, the study has 80% power to detect 30% vs. 10% or 90% power to detect 25% vs 5% in RR between the two dose levels at the 10% type I error rate (one-sided). A p-value of 10% approximately corresponds to a 12% empirical difference in RR.

With 44 patients treated at a dose level, the study has 89% power to test the null hypothesis of RR=10% at 2.5% type I error rate (one-sided) when the true RR is 30%. A p-value of 2.5% approximately corresponds to an empirical RR of 23% (10/44).

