Based on preliminary data from the non-randomized patients, the RR appears similar between the ipilimumab-refractory population and the ipilimumab-naïve population. A pooled analysis of the PD-L1 high patients from Part B (randomized) and Part D (randomized) will be conducted. It is expected that 50 to 75 PD-L1 high patients will be treated at a dose level in the pooled analysis. With this sample size, the study has >95%

power to reject the null hypothesis of 10% RR at type I error rate of 2.5% (one-sided) when the true RR is 30%.

Part B enrolled after Amendment 04 (randomized: 10 mg/kg Q3W vs 10 mg/kg Q2W)

A total of approximately 230 patients will be randomized 1:1 to 10 mg/kg Q3W or 10 mg/kg Q2W, stratified by ipilimumab-naïve vs non ipilimumab-naïve. Based on preliminary data from non-randomized patients, the RR appears similar between the non ipilimumab-naïve population and the ipilimumab-naïve population. The primary analysis of this cohort is based on a pooled analysis, stratified by ipilimumab treatment history. Subgroup analyses will also be conducted. With 230 patients, the study has ~85% power to detect a 20% difference (i.e., 30% vs 50%) in RR between the two doses at the 2.5% type I error rate (one-sided). A p-value of 2.5% approximately corresponds to a 13% empirical difference in RR.

Similar to randomized cohorts in Part B and Part D between 10 mg/kg Q3W vs 2 mg/kg Q3W, anti-tumor activities of pembrolizumab (MK-3475) at a dose schedule as well as related to PD-L1 expression will also be investigated.

Part F NSCLC 1L PD-L1 positive (randomized)

With 44 patients per dose level, the study has 86% power to detect a 25% difference in RR (i.e., 45% vs 20%) at $\alpha=10\%$ (1-sided) between two dose levels. A p-value of 10% approximately corresponds to a 13% empirical difference in RR.

With 44 1L patients treated at a dose level, the study has 91% power to test the null hypothesis of $RR=25\%$ at 2.5% type I error rate (one-sided) when the true RR is 50%. A p-value of 2.5% approximately corresponds to an empirical RR of 41% (18/44).

Part F NSCLC 3L+ (single arm)

With 32 3L+ patients treated at 10 mg/kg, the study has 90% power to test the null hypothesis of $RR=10\%$ at 2.5% type I error rate (one-sided) when the true RR is 35%. A p-value of 2.5% approximately corresponds to an empirical RR of 25% (8/32).

Part F NSCLC 3L+ PD-L1 negative (single arm)

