With 40 patients treated at 10 mg/kg Q2W, the study has >90% power to rule out a >30% RR if <8 patients respond (i.e., probability of observing < 8 responses is <10% when true RR is 30%).

Part F NSCLC 2L+ PD-L1 positive (single arm)

With 40 patients treated at 2 mg/kg Q3W, the study has ~90% power to test the null hypothesis of RR =10% at 2.5% type I error rate (one-sided) when the true RR is 30%. A p-value of 2.5% approximately corresponds to an empirical RR of 22.5% (9/40).

Part F NSCLC 2L+ PD-L1 positive (randomized)

Approximately 250 patients will be randomized (3:2) to 10 mg/kg Q3W and 10 mg/kg Q2W. The randomization may be stratified by PD-L1 expression level based on a preliminary cutoff point once available (see Section 3.5.5.4 for details). With 250 patients, the study has approximately 95% power to detect a 15% difference in RR between the two doses at type I error rate of 10% (one-sided) assuming that the RR at 10 mg/kg Q3W is 10%.

Enrollment of patients with weakly positive tumors will be capped at 50% so that at least 75 patients with strongly positive tumors will be treated at 10 mg/kg Q3W. With 75 patients treated at 10 mg/kg Q3W, the study has 85% power to detect a 15% difference in RR between pembrolizumab (MK-3475) and historical control which is conservatively estimated to be 15% (i.e., 30% vs 15%) at type I error rate of 2.5% (one-sided). A p-value of 2.5% approximately corresponds to an empirical RR of 25% (i.e., the lower bound of the 95% CI for an empirical RR at 25% will exclude 15%). With 50 patients at 10 mg/kg Q2W, the study has 68% (or 89%) power to detect a 15% (or 20%) difference in RR between pembrolizumab (MK-3475) and historical control at type I error rate of 2.5% (one-sided). A p-value of 2.5% approximately corresponds to an empirical RR of 28% (i.e., the lower bound of the 95% CI for an empirical RR at 28% will exclude 15%). If 10 mg/kg Q2W has comparable anti-tumor effect to 10 mg/kg Q3W in the population, the two doses will be pooled for a joint analysis as appropriate. Regardless, if the primary analysis in the biomarker strongly positive population is positive a step-down analysis will be performed to assess all biomarker positive patients including patients with weakly positive tumors.

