after the randomization. The final PD-L1 assay cutoff point for efficacy analyses will be determined before this IA will occur. The target response rate is 20% for interim futility decisions. As guidance, if less than 3 out of 30 patients with weakly positive tumors (i.e., <10%) have a confirmed response no further patients with weakly positive tumors (based on final cutoff point) will be enrolled. The probability of observing less than 3 responses is <4% when the true response rate is 20%. When sample sizes are slightly different, an empirical response rate of <10% will be used as a reference or futility decisions which will also take into account the totality of data. Because the two dose schedules may have different cutoff points, a subgroup analysis by dose schedule will be conducted to determine whether to exclude patients with weakly positive tumors for one schedule or for both (see Section 3.5.5.4 for more details).

Additional Interim Analyses

In addition to the above interim analyses, an interim analysis of Part C may be conducted after all patients have had a 3-month follow-up, interim analyses of Part B ipilimumab-refractory patients and Part D ipilimumab-naive patients (timings to be determined) may be conducted to assist with the dose-selection decision for planning phase 2 studies in melanoma patients, and interim analyses may also be conducted to determine the cutoff points for high PD-L1 patients in melanoma and NSCLC patients (see Section 3.5.5.4).

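### The roughly 95% power for the F-2 Q3W versus Q2W comparison rests on a 10% response rate for the Q3W arm that cannot hold together with the 30% planned for at least half of that arm

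*Combined protocol and SAP*

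**What the plan says.** Section 3.5.7 (Part F NSCLC 2L+ PD-L1 positive, randomized) sets the size and the power of the schedule comparison: "Approximately 250 patients will be randomized (3:2) to 10 mg/kg Q3W and 10 mg/kg Q2W", and "the study has approximately 95% power to detect a 15% difference in RR between the two doses". The error rate and the assumed Q3W rate behind that power are given in the same sentence: "at type I error rate of 10% (one-sided) assuming that the RR at 10 mg/kg Q3W is 10"%. Section 3.5.6 confirms the error rate: "Between-dose comparisons are all conducted at 20% (two-sided), or equivalent 10% (one-sided) for sample size and power calculation purpose below", with one Part B comparison excepted.

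The following paragraph of 3.5.7 caps weakly positive tumors at 50%, so that at least 75 strongly positive patients receive Q3W. It powers that group against a "historical control which is conservatively estimated to be 15% (i.e., 30% vs 15"%).

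The only response rate attached to weakly positive patients is in section 3.5.9: "The target response rate is 20% for interim futility decisions". The same 2L+ text of 3.5.7 provides that the two schedules may be pooled if Q2W has an effect comparable to Q3W, and gives no numerical criterion.

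The sample size also differs between sections. Sections 1.5 and 2.4.1 plan 280 randomized patients (168 Q3W, 112 Q2W), while 3.5.5.4 and 3.5.7 use 250.

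**The concern.** The two planning rates refer to the same arm. If at least half of the Q3W patients respond at 30%, the arm as a whole cannot respond at 10%, whatever happens in the other half. Binomial variance rises as the response rate moves from 10% towards 50%. A fixed 15-point advantage for Q2W is therefore easiest to detect from a low starting rate, and the 10% assumption gives the most favorable figure.

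What is at stake is how a null result is read. The comparison informs the choice of schedule, and a judgment that the schedules are comparable opens the way to pooling them. A reader who relies on the stated power would put the chance of missing a 15-point advantage of Q2W at about 5%.

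**Working it through.** **Inputs.** From 3.5.7: 250 patients randomized 3:2, hence 150 Q3W and 100 Q2W; a 15-point difference; one-sided 10%; Q3W RR 10%; strongly positive share at least 75/150 = 50%; strongly positive RR 30%. From 3.5.9: a 20% target for weakly positive patients, used for futility only. From 2.4.1: 168 and 112 patients as the alternative arm sizes.

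**Step 1: reproduce the stated power.** The plan names no test, so two were tried at 10% versus 25% with 150/100.

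- Pooled Z. The pooled rate is (150 × 0.10 + 100 × 0.25)/250 = 0.16. The standard error under the null is √[0.16 × 0.84 × (1/150 + 1/100)] = 0.0473. Under the alternative it is √(0.10 × 0.90/150 + 0.25 × 0.75/100) = 0.0497. Power = Φ[(0.15 − 1.2816 × 0.0473)/0.0497] = Φ(1.80) = 96.4%.
- Fisher's exact test, enumerating all outcomes: 95.3%.

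Both agree with the stated figure of about 95%. Fisher is closer here. It also gives 84.9% for "the study has ~85% power to detect a 20% difference (i.e., 30% vs 50%) in RR" in the Part B schedule comparison (115 per arm, one-sided 2.5%), where pooled Z gives 87.7%. Fisher is therefore used as the like-for-like method below.

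**Step 2: the Q3W rate implied by the next paragraph.** With strongly positive share s and weakly positive rate w, the arm's rate is s × 30% + (1 − s) × w.

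- s = 0.5, w = 0%: 15%, the lowest possible value.
- s = 0.5, w = 20%: 25%.
- s = 1, or w = 30%: 30%.

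Conversely, an arm-level rate of 10% with s = 0.5 needs a strongly positive rate of at most 20%, because 0.5 × 20% + 0.5 × 0% = 10%.

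**Step 3: power for a 15-point advantage of Q2W, one-sided 10%.**

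| Q3W vs Q2W RR | Fisher 150/100 | Pooled Z 150/100 | Fisher 168/112 | Pooled Z 168/112 |
|---|---|---|---|---|
| 10% vs 25% (as stated) | 95.3% | 96.4% | 96.9% | 97.6% |
| 15% vs 30% | 91.6% | 93.6% | 94.1% | 95.4% |
| 20% vs 35% | 88.5% | 91.0% | 91.5% | 93.2% |
| 25% vs 40% | 86.1% | 88.8% | 89.3% | 91.3% |
| 30% vs 45% | 84.2% | 87.2% | 87.6% | 89.9% |

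**Step 4: the other direction.** Section 3.5.6 makes the comparison two-sided at 20%, so Q2W may also be the worse schedule. With 150/100, Fisher power is 95.4% at Q3W 25% versus Q2W 10%, and 91.9% at 30% versus 15%.

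**The case against.** The strongest reply is that the plan makes two separate conditional statements. The 95% is explicitly conditional on a 10% Q3W rate and is right on that condition. The 30% is the alternative of a single-arm test against a historical control, not a forecast. Ten percent is also not foreign to the plan: it is the null rate for the F-3 cohort and for the 3L+ cohort. All of this stands. A reader might infer a calculation error, and there is none. The difficulty is only that the two assumptions cannot describe one arm at the same time.

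It is also fair that the size of the loss depends on choices the plan leaves open. It is smaller with 280 patients, smaller by about 1 to 3 points with pooled Z, and absent at 25% versus 10% in favor of Q3W. The 91.6% end requires that no weakly positive patient responds, which the plan states nowhere. The 20% used for the 25% scenario is a futility target rather than an expected rate.

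A reader might extend the point to melanoma, since for Part D "the study has 80% power to detect 30% vs. 10% or 90% power to detect 25% vs 5% in RR" while a later Part B cohort is planned at 30% versus 50%. The documents do not support that. Part D's 10% and 30% are its own single-arm null and alternative. The ipilimumab-refractory comparison likewise sets the inferior arm at its 10% null and the better arm at its 25% alternative. Each is coherent within its cohort. The 30% versus 50% belongs to a different population, amendment and error rate.

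Nor does the plan say that a non-significant comparison counts as comparable. The pooling clause leaves the matter to judgment.

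**Conclusion.** The point holds as an inconsistency between planning assumptions. The 10% rate for the whole Q3W arm is incompatible with 30% in a strongly positive group that makes up at least half of it. On rates consistent with that 30%, power to detect a 15-point advantage of Q2W is 84% to 92% by Fisher with 150/100, or 88% to 94% with 168/112, against the stated 95%. At a Q3W RR of 25% to 30%, the chance of missing such an advantage is 14% to 16% with 150/100, or 11% to 12% with 168/112, rather than about 5%.

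This rests on taking the 30% alternative at face value, on a strongly positive share of at least 50%, and on Q2W being the better schedule. Power exceeds 80% in every whole-cohort scenario examined, so the adequacy of the design is not in question. What needs correcting is a planning figure that is too favorable for reading a null schedule comparison.

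**What to change.** In the 2L+ randomized paragraph of 3.5.7, replace the single 95% figure with power over a Q3W RR of 15% to 30% (for example 15%, 25% and 30%), with Q2W better and with Q2W worse. Name the test. Reconcile the randomized number (250 in 3.5.5.4 and 3.5.7, 280 in 1.5 and 2.4.1) and use the agreed figure. Quote the resulting range wherever the two schedules are judged comparable for pooling. The Part D and ipilimumab-refractory power statements need no change on this ground.

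The cost is a text edit and a somewhat less favorable stated power. Sample size, allocation and error rate are unaffected.
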